#### 8.2.1.3 Mucositis

For **grade 3 mucositis**, delay 5FU and oxaliplatin until recovery to grade  $\leq 1$ , then resume oxaliplatin at the same dose level and 5FU at the next lower dose level.

For **grade 4 mucositis**, delay 5FU and oxaliplatin until recovery to grade  $\leq 1$ , then resume 5FU and oxaliplatin at the next lower dose level.

#### 8.2.1.4 Neuropathy (Sensory or Motor)

Toxicity Scale for the Sensory Neuropathies Associated with Oxaliplatin (using the Oxaliplatin Specific Neurotoxicity Scale)

	Symptoms
Grade 1	Paresthesias/dysesthesias* of short duration that resolve and do not interfere with function.
Grade 2	Paresthesias/dysesthesias* interfering with function, but not with activities of daily living (ADL)
Grade 3	Paresthesias/dysesthesias* with pain or with functional impairment that also interfere with ADL.
Grade 4	Persistent paresthesias/dysesthesias* that are disabling or life threatening.
	* May be cold-induced

For **grade 2 neurotoxicity persisting between treatments**, continue mFOLFOX6 with one dose level reduction of oxaliplatin for all subsequent cycles.

For **grade 3 neurotoxicity resolving to grade  $\leq 2$  between treatments**, continue mFOLFOX6 with one dose level reduction of oxaliplatin for all subsequent cycles.

For **grade 3 neurotoxicity persisting between treatments**, discontinue oxaliplatin.

For **grade 4 neurotoxicity**, discontinue oxaliplatin.

For **laryngopharyngeal dysesthesia**, increase the duration of oxaliplatin infusion to 6 hours for all subsequent cycles.

#### 8.2.1.5 Hepatobiliary Toxicity

For **grade 3 or 4 bilirubin increased**, delay 5FU and oxaliplatin until recovery to grade  $\leq 1$ , then resume 5FU and oxaliplatin at the next lower dose level.

For **grade 3 or 4 ALT/AST increased**, discontinue 5FU and oxaliplatin.

**8.2.1.6 Renal Insufficiency**

For **grade 3 or 4 creatinine increased and NOT attributed to study treatment**, delay 5FU and oxaliplatin until grade  $\leq 1$ , then restart at the same doses.

**8.2.1.7 Pulmonary Toxicities**

For  **$\geq$  grade 3 cough, dyspnea, hypoxia, pneumonitis, or pulmonary infiltrates**, delay oxaliplatin until interstitial lung disease is ruled out. Continue 5FU/leucovorin. Discontinue all protocol therapy if interstitial lung disease is confirmed.

**8.2.1.8 Thrombotic Microangiopathy**

For  **$\geq$  grade 3 hemolytic uremic syndrome (HUS)**, discontinue oxaliplatin.

**8.2.1.9 Cardiovascular Toxicities**

For **grade 3 or 4 myocardial infarction**, discontinue mFOLFOX6.

For **grade 2 ischemia cerebrovascular**, discontinue mFOLFOX6.

**8.2.2 Dose Modifications for Atezolizumab**

Administration of atezolizumab will be performed in a setting with emergency medical facilities and staff who are trained to monitor for and respond to medical emergencies.

Premedication is not permitted for the first dose of atezolizumab. Premedication with antihistamines or antipyretics/analgesics (e.g., acetaminophen) may be administered for subsequent infusions at the discretion of the treating physician. The management of Infusion Related Reactions will be according to severity as follows:

- In the event that a patient experiences a Grade 1 Infusion Related Reaction during Cycle 1, the infusion rate should be reduced to half the rate being given at the time of event onset. Once the event has resolved, the investigator should wait for 30 minutes while delivering the infusion at the reduced rate. If tolerated, the infusion rate may then be increased to the original rate.
- In the event that a patient experiences a Grade 2 Infusion Related Reaction, or flushing, fever, or throat pain, the infusion should be immediately interrupted and the patient should receive aggressive symptomatic treatment. The infusion should be restarted only after the symptoms have adequately resolved to baseline grade. The infusion rate at restart should be half of the infusion rate that was in progress at the time of the onset of the Infusion Related Reaction. For subsequent infusions, administer oral premedication with antihistamine and anti-pyretic and monitor closely for Infusion Related Reactions.
- For Grade 3 or 4 Infusion Related Reactions, the infusion should be stopped immediately, and aggressive resuscitation and supportive measures should be initiated (e.g., oral or IV antihistamine, anti-pyretic, glucocorticoids, epinephrine, bronchodilators, oxygen). Atezolizumab should be permanently discontinued. Resumption of atezolizumab may be considered in patients who are deriving benefit and have fully recovered from the immune-related event; retreatment requires consultation with, and consent of, the trial Principal Investigator (PI).

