Chemotherapy and immunotherapy must be administered at the registering institution, including the one cycle of mFOLFOX6 the patient may have received prior to registration. Treatment will continue until disease recurrence or unacceptable adverse event or inability to tolerate treatment occurs (despite all allowed dose reductions). Otherwise treatment will continue until completion of the full treatment program and entrance onto clinical follow-up. Also, see [Section 12.0](#) for additional information regarding discontinuation of treatment. Administration of atezolizumab should be performed in a setting with emergency medical facilities and staff who are trained to monitor for and respond to medical emergencies.

The initial dose of atezolizumab will be delivered over 60 ( $\pm$ 15) minutes. If the first infusion is tolerated without infusion associated AEs, the second infusion may be delivered over 30 ( $\pm$ 10) minutes. If the 30-minute infusion is well tolerated, all subsequent infusions may be delivered over 30 ( $\pm$ 10) minutes. For the first infusion, the patient's vital signs (heart rate, respiratory rate, blood pressure, and temperature) should be determined within 60 minutes before, during (every 15 [ $\pm$ 5] minutes), and 30 ( $\pm$ 10) minutes after the infusion. For subsequent infusions, vital signs should be collected within 60 minutes before and within 30 minutes after the infusion. Vital signs should be collected during the infusion only if clinically indicated. Patients should be informed about the possibility of delayed post-infusion symptoms and instructed to contact their study physician if they develop such symptoms.

No premedication will be allowed for the first dose of atezolizumab. Premedication may be administered for Cycles  $\geq 2$  at the discretion of the treating physician.

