### 7.1 Arm 1: mFOLFOX6 Plus Atezolizumab

The agents in the table below are listed in the order of intended administration.

Agent	Dose	Route	Duration	Days	Cycle
Atezolizumab	840mg*	IV	Over 60 min (+/- 15 min) for 1 st dose, then Over 30min (+/- 10 min) for all subsequent doses	Day 1	Every 14 days
Oxaliplatin	85mg/m 	IV	Over 2 hours (+/- 30 min)	Day 1	Every 14 days
Leucovorin**	400mg/m 	IV	Over 2 hours (+/- 30 min)	Day 1	Every 14 days
Fluorouracil	400mg/m  + 2400mg/m 	IV	Bolus + Over 46 hours (+/- 4 hours)	Day 1 + Days 1-3	Every 14 days

\* Patients 12 to < 18 years of age will receive a dose of 10 mg/kg up to a maximum flat dose of 840 mg. The patient's age on the day of treatment should be used to determine whether to use weight-based dosing.

\*\* Alternatively, leucovorin may be administered (via separate infusion containers) concurrently with oxaliplatin. Infusion duration may be adjusted according to institutional practice.

Note: If the minimum durations are followed and/or concurrent administration of leucovorin and oxaliplatin occurs, then fluorouracil administration could be completed on Days 1-2.

Atezolizumab should be the first drug administered regardless of cycle number as no premedication is allowed prior to the first dose of atezolizumab; see [Section 7.0](#) and [Section 8.1.4](#) for additional details.

Patients should receive 6 months (12 cycles total) of mFOLFOX6, including the cycle that may have been received prior to registration.

**For patients who started mFOLFOX6 after registration**, atezolizumab should start on Day 1 Cycle 1 of mFOLFOX6 (12 cycles in combination with mFOLFOX6 followed by 13 cycles as monotherapy for a total of 25 cycles of atezolizumab).

**For patients who receive one cycle of mFOLFOX6 prior to registration**, atezolizumab should start on Day 1 Cycle 2 of mFOLFOX6 (11 cycles in combination with mFOLFOX6 followed by 13 cycles as monotherapy for a total of 24 cycles of atezolizumab).

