#### Infusion-Related Reactions and Cytokine-Release Syndrome

No premedication is indicated for the administration of Cycle 1 of atezolizumab. However, patients who experience an infusion-related reaction (IRR) or cytokine-release syndrome (CRS) with atezolizumab may receive premedication with antihistamines, antipyretics, and/or analgesics (*e.g.*, acetaminophen) for subsequent infusions. Metamizole (dipyrone) is prohibited in treating atezolizumab-associated IRRs because of its potential for causing agranulocytosis.

IRRs are known to occur with the administration of monoclonal antibodies and have been reported with atezolizumab. These reactions, which are thought to be due to release of cytokines and/or other chemical mediators, occur within 24 hours of atezolizumab administration and are generally mild to moderate in severity.

CRS is defined as a supraphysiologic response following administration of any immune therapy that results in activation or engagement of endogenous or infused T cells and/or other immune effector cells. Symptoms can be progressive, always include fever at the onset, and may include hypotension, capillary leak (hypoxia), and end-organ dysfunction (Lee *et al.*, 2019). CRS has been well documented with chimeric antigen receptor T-cell therapies and bispecific T-cell engager antibody therapies but has also

been reported with immunotherapies that target PD-1 or PD-L1 (Rotz *et al.*, 2017; Adashek and Feldman 2019) including atezolizumab.

There may be significant overlap in signs and symptoms of IRRs and CRS, and in recognition of the challenges in clinically distinguishing between the two, consolidated guidelines for medical management of IRRs and CRS are provided in the table below.

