#### Management Guidelines for Infusion-Related Reactions and Cytokine-Release Syndrome

Event	Management
Grade 1 a Fever b with or without constitutional symptoms	
 
• Immediately interrupt infusion.
 
• Upon symptom resolution, wait 30 minutes and then restart infusion at half the rate being given at the time of event onset.
 
• If the infusion is tolerated at the reduced rate for 30 minutes, the infusion rate may be increased to the original rate.
 
• If symptoms recur, discontinue infusion of this dose.
 
• Administer symptomatic treatment,c including maintenance of IV fluids for hydration.
 
• In case of rapid decline or prolonged CRS (> 2 days) or in patients with significant symptoms and/or comorbidities, consider managing as per Grade 2.
 
• For subsequent infusions, consider administration of oral premedication with antihistamines, anti-pyretics, and/or analgesics, and monitor closely for IRRs and/or CRS.
 

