Grade 2 a Fever b with hypotension not requiring vasopressors and/or Hypoxia requiring low-flow oxygen d by nasal cannula or blow-by	
 
• Immediately interrupt atezolizumab infusion.
 
• Upon symptom resolution, wait for 30 minutes and then restart infusion at half the rate being given at the time of event onset.
 
• If symptoms recur, discontinue infusion of this dose.
 
• Administer symptomatic treatment.c
 
• For hypotension, administer IV fluid bolus as needed.
 
• Monitor cardiopulmonary and other organ function closely (in the ICU, if appropriate). Administer IV fluids as clinically indicated and manage constitutional symptoms and organ toxicities as per institutional practice.
 
• Rule out other inflammatory conditions that can mimic CRS (e.g., sepsis). If no improvement within 24 hours, initiate workup and assess for signs and symptoms of HLH or MAS.
 
• Consider IV corticosteroids (e.g., methylprednisolone 2 mg/kg/day or dexamethasone 10 mg every 6 hours).
 
• Consider anti-cytokine therapy.c
 
• Consider hospitalization until complete resolution of symptoms. If no improvement within 24 hours, manage as per Grade 3, that is, hospitalize patient (monitoring in the ICU is recommended), permanently discontinue atezolizumab.
 
• If symptoms resolve to Grade 1 or better for 3 consecutive days, the next dose of atezolizumab may be administered. For subsequent infusions, consider administration of oral premedication with antihistamines, anti-pyretics, and/or analgesics and monitor closely for IRRs and/or CRS.
 
• If symptoms do not resolve to Grade 1 or better for 3 consecutive days, contact the Principal Investigator.
 

Grade 3 a Fever b with	
 
• Permanently discontinue atezolizumab.
 
• Administer symptomatic treatment.c
 
• For hypotension, administer IV fluid bolus and vasopressor as needed.
 

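### Section 8.2.2 holds two overlapping, unreconciled rule sets for atezolizumab infusion reactions, which differ on fever, Grade 2 escalation and Grade 3–4 rechallenge

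*Combined protocol and SAP*

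**What the plan says.** Section 8.2.2 (Dose Modifications for Atezolizumab) opens with three bullets on infusion-related reactions (IRRs).

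- **Grade 1:** when a patient "experiences a Grade 1 Infusion Related Reaction during Cycle 1, the infusion rate should be reduced to half the rate being given" at onset. The 30-minute wait after resolution is spent infusing at that reduced rate.
- **Grade 2 and fever:** "In the event that a patient experiences a Grade 2 Infusion Related Reaction, or flushing, fever, or throat pain, the infusion should be immediately interrupted". The infusion restarts at half rate, and premedication is directed for later infusions.
- **Grade 3–4:** atezolizumab is stopped permanently. The bullet then adds that "Resumption of atezolizumab may be considered in patients who are deriving benefit and have fully recovered from the immune-related event", subject to the consent of the trial Principal Investigator (PI).

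Later in the same section, the text on IRRs and cytokine-release syndrome (CRS) announces that "consolidated guidelines for medical management of IRRs and CRS are provided in the table below". In that table the Grade 1 row begins "Immediately interrupt infusion". The Grade 2 row says that a patient not improved by 24 hours is managed as Grade 3, with the instruction to "permanently discontinue atezolizumab". The Grade 3 and Grade 4 rows both open with a permanent stop and give no way back.

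On infusion time, the dosing table in Section 7.1 gives 60 minutes for the first dose, "then Over 30min (+/- 10 min) for all subsequent doses". Section 7.0 is conditional: "If the first infusion is tolerated without infusion associated AEs, the second infusion may be delivered over 30" minutes. Section 10.5 also ties the shorter time to a tolerated first infusion.

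**The concern.** Both texts are current, both apply to IRRs, and neither refers to the other. Two sites can each follow the protocol and still treat a similar reaction differently: one premedicates from then on and the other only considers it; one stops atezolizumab for good after a Grade 2 reaction that is slow to settle and the other has no such instruction; one asks the trial PI about resuming after a Grade 3–4 reaction and the other sees no route to ask.

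This bears on patient safety first. It also bears on the data. Whether an action was a protocol deviation, and whether a stop was required or elective, depends on which part of Section 8.2.2 the site used. The German appendix carries the ambiguity over, because its Section 1.3 ties permanent discontinuation for toxicity to Section 8.2.

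**Working it through.** There is no planned figure to reproduce, so the check is a comparison of the texts.

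**Step 1. Do the two texts cover the same reactions?** Yes. The table is introduced as covering IRRs and CRS together, because the two overlap clinically. It cannot be read as a CRS-only table.

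**Step 2. Do they grade the same way?** Not demonstrably. The table's notes say that management follows ASTCT consensus grades for CRS, while severity is reported by CTCAE. The bullets name no scale. All four grade rows of the table are defined by fever plus, from Grade 2 up, hypotension or hypoxia.

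**Step 3. Compare reaction by reaction.**

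| Reaction | Bullets | IRR/CRS table |
|---|---|---|
| Fever | Handled with Grade 2. Interrupt, restart at half rate. Later premedication directed. Return to full rate not addressed. | Grade 1. Interrupt, restart at half rate. Full rate allowed after 30 minutes tolerated. Later premedication to be considered. |
| Grade 2 | Interrupt, restart at half rate. Later premedication directed. No 24-hour step. | Interrupt, restart at half rate. Later premedication to be considered. Not improved at 24 hours: permanent stop. |
| Grade 3–4 | Permanent stop, then possible resumption with the trial PI's consent. | Permanent stop. No resumption route stated. |
| Grade 1, Cycle 1 | Halve the rate and keep infusing. | Interrupt, but the row is defined by fever. |

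For fever the two texts agree on interruption and on the half-rate restart. They part on grade, on return to full rate and on premedication. For Grade 2 they part on premedication and on the 24-hour step. For Grade 3–4 they agree on the stop and part only on what may follow. For a Grade 1 reaction without fever, flushing or throat pain, the bullet applies in Cycle 1 while the table's Grade 1 row, read literally, does not describe the patient. Which text governs is therefore unclear.

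**Step 4. Does silence on resumption in the table carry meaning?** Probably. The neurologic table in the same section states a resumption exception in its footnote c, in nearly the wording of the Grade 3–4 infusion bullet. The protocol therefore writes the exception where it intends one. The bullet also speaks of recovery from an immune-related event although its subject is an infusion reaction, which suggests text carried over from elsewhere. That last step is inference.

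**Step 5. Is there a rule of precedence?** None was found in the general adverse-event guidelines of Section 8.2.2, in its subsection on specific events, in Section 10.5 or in the German appendix. The specific-events subsection sends the reader, for infusion reactions, to a further table on first and subsequent infusions. No table of that name is in the supplied text.

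**Step 6. Infusion time.** The Section 7.1 cell carries no condition, while Sections 7.0 and 10.5 do. After a first infusion that was not tolerated, the three places do not give one answer.

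**Step 7. Size.** The documents give no rate of IRRs by grade, by presence of fever, or by cycle. The number of Arm 1 patients who would meet a rule on which the texts differ cannot be computed.

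**The case against.** The strongest reply is that much of the apparent conflict comes from two grading scales, and that the two texts agree on the main actions. Most of this stands, and it rules out three stronger readings.

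*Slow versus interrupt at Grade 1.* A reader might infer a flat contradiction for the same patient. The documents do not show that. The bullet is limited to Cycle 1. The table's Grade 1 row requires fever, and the bullets themselves send fever to interruption. What remains is uncertainty over afebrile Grade 1 reactions.

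*No further doses versus all remaining doses at Grade 3–4.* A reader might infer that one text stops treatment while the other lets sites continue. Both order a permanent stop. The exception in the bullets is discretionary and needs the trial PI's consent, so a site cannot act on it alone. The table is silent and does not prohibit resumption.

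*A patient count.* The list of atezolizumab risks in Section 9.4 places infusion-related reactions in the column for up to 20%, without the mark for events under 3%. Applied to 350 adult Arm 1 patients, that gives 0.03 × 350 = 10.5 to 0.20 × 350 = 70. At 24 to 25 infusions each, planned exposure is 350 × 24 = 8,400 to 350 × 25 = 8,750 infusions. Neither range measures the conflict: the first counts reactions of every grade and the second counts infusions.

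Two smaller replies also have weight. The Section 7.1 cell may be only a summary of Section 7.0. The table that could not be found may sit in an external document, since the sentence before the reference points to the Investigator's Brochure; its absence here is not proof of a defect.

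The scale argument does not dispose of the point. It explains part of the mismatch, but the table is expressly applied to IRRs and sites are not told how to choose. It does not account for the Grade 3–4 difference on resumption, nor does it tell a site whether the 24-hour step applies.

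**Conclusion.** The inconsistency is real but narrower than two opposed rule sets. Section 8.2.2 gives differing instructions on four matters: grading of fever, with its consequences for full rate and premedication; premedication and the 24-hour permanent stop at Grade 2; resumption after Grade 3–4; and which rule covers an afebrile Grade 1 reaction in Cycle 1. The infusion-time statements and the unlocated table are separate, lesser points.

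The consequence is inconsistent safety handling and inconsistent atezolizumab discontinuation decisions in Arm 1. No patient number can be attached to it. The primary analysis is by intention to treat, and its design figures (165 DFS events, hazard ratio 0.6, 90% power) do not depend on this text.

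The conclusion assumes that no document outside the supplied text, such as the Investigator's Brochure or site guidance, sets an order of precedence. It takes no view on which clinical rule is right.

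**What to change.** Reconcile the opening bullets of Section 8.2.2, its IRR/CRS text and table, its subsection on specific events, and the infusion-time statements in Sections 7.0, 7.1 and 10.5 into one rule set. That rule set should:

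- name one grading scale for management, and say how reactions without fever are classified;
- give one statement each on fever, on premedication after a reaction, and on the 24-hour step at Grade 2;
- say explicitly whether resumption after Grade 3–4 is possible and, if so, on whose authority;
- give one statement on the duration of later infusions;
- supply, locate or remove the further infusion table that is cited.

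The sponsor decides the clinical content.

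The cost is protocol wording in the next update, with no new procedures or data. The German appendix projected its last treatment for February 2023; the documents do not say whether dosing has ended across the trial. If it has, the remaining step is to state, when discontinuations are reported, which text sites were told to follow.

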**General AE Management and Dose Modification Guidelines**

There will be no dose reduction for atezolizumab in this study.

Patients may temporarily suspend study treatment for up to 84 days (12 weeks) beyond the scheduled date of delayed infusion if study drug-related toxicity requiring dose suspension is experienced. If atezolizumab is held because of AEs for 84 days beyond the scheduled date of infusion, the patient will be discontinued from atezolizumab and will be followed for safety and efficacy as specified in this protocol. If the AE resolves within 84 days and the patient is receiving corticosteroid therapy for the event, atezolizumab may be held for longer than 84 days (up to 4 weeks) in order to allow tapering of the steroid dose to  $\leq 10$  mg oral prednisone or equivalent.

Dose interruptions for reasons other than toxicity, such as surgical procedures, may be allowed. The acceptable length of interruption will be at the discretion of the study PI in consultation with CTEP.

The primary approach to grade 1 to 2 irAEs is supportive and symptomatic care with continued treatment with atezolizumab; for higher-grade irAEs, atezolizumab should be withheld and oral and/or parenteral steroids administered. Recurrent grade 2 irAEs may also mandate withholding atezolizumab or the use of steroids. Assessment of the benefit risk balance should be made by the investigator, with consideration of the totality of information as it pertains to the nature of the toxicity and the degree of clinical benefit a given patient may be experiencing prior to further administration of atezolizumab. Atezolizumab should be permanently discontinued in patients with life threatening irAEs.

